##### **3.2.2 Relative day**

The relative day of a visit or an event with respect to the first intake of LCM will be presented in subject data listings. Relative day will be calculated as follows:

- If the visit/event date occurred prior to the first intake of LCM, the relative day is calculated as visit/event date minus first LCM dose date. In subject data listings, relative days based on this situation will be preceded by a ‘-’.

- If the visit/event date occurred on or after the first intake of LCM but prior to the last dose of LCM, the relative day is calculated as visit/event date minus first LCM dose date + 1.
- If the visit/event date occurred after the date of last dose of LCM, the relative day is calculated as visit/event date minus last dose date. In subject data listings, relative days based on this situation will be preceded by a '+’.

Relative days will not be presented for partial or missing dates.

### 3.2.3 Study periods

For the purpose of analyses, the following periods are defined.

- Baseline Period:

The Baseline Period is defined as the period of time from the date of Visit 1 to 1 day prior to the date of first dose of LCM. For the definition of Baseline values see Section 3.3.

- Titration Period:

The Titration Period is defined as the period of time from the date of first dose of LCM to the date of Visit 6 or the date of ET, whatever occurs first. If Visit 6 and ET are missing the Titration Period ends at the date of last dose of LCM.

- Maintenance Period:

The Maintenance Period is defined as the period of time from the day after the date of Visit 6 to the date of Visit 9/ET. If Visit 9/ET is missing the Maintenance Period ends at the date of last dose of LCM.

- Treatment Period:

The Treatment Period is defined as the combined Titration and Maintenance Period, ie, starts at the date of first dose of LCM and ends at Visit 9/ET. If Visit 9/ET is missing the Maintenance Period ends at the date of last dose of LCM.

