Lacosamide belongs to a novel class of functionalized amino acids. It has minimal protein binding and effect on cytochrome P450 enzyme system function (reducing the risk of drug-drug interactions), high oral bioavailability, and a half-life of approximately 13 hours (in adults), which allows a twice daily (bid) dose regimen. It also displays dose-proportional PK following administration over a range of doses up to 800mg in adults. Lacosamide's mode of action is proposed to be mediated by a selective enhancement of slow inactivation of voltage-gated sodium channels which may explain the immediate anticonvulsant effects of LCM (Errington et al, 2008).

Lacosamide has been approved as adjunctive therapy in the treatment of partial-onset seizures with or without secondary generalization in patients 16 years of age and older in the EU (oral tablets, oral solution, and solution for intravenous [iv] infusion) and as adjunctive therapy in the treatment of partial-onset seizures in patients 17 years of age and older in the USA (oral tablets, oral solution, and solution for iv infusion). The oral solution and the film-coated tablet formulations are suitable for oral administration to pediatric patients.

Bioequivalence has been shown between the tablet and oral solution formulations, comparing 2 tablets of LCM 100mg and the oral solution containing LCM 200mg, after single-dose administration in healthy subjects. The PK of LCM and its major metabolite, SPM 12809 (O-desmethyl-LCM), in plasma, urine, and saliva were identical or very similar after single oral doses of LCM 200mg administered as tablets or as oral solution.

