6.3 Withdrawal criteria

Subjects are free to withdraw from the study at any time, without prejudice to their continued care.

All subjects who withdraw from the study due to an AE must be followed until resolution of the event or until the event is considered stable.

Subjects **must** be withdrawn from the study if any of the following events occur:

1. Subject experiences intolerable AEs, including clinically relevant abnormal laboratory findings that, in the opinion of the investigator, preclude further participation in the study.
2. The sponsor or a regulatory agency requests withdrawal of the subject.
3. Female subject achieves menarche and does not practice contraception as provided in Exclusion Criterion 21, unless sexually abstinent.
4. Subject becomes pregnant, as evidenced by a positive pregnancy test.
5. Subject has QTc interval of ≥ 500 ms that is confirmed by a cardiologist overread on any ECG.
6. Subject develops second- or third-degree AV block.
7. Subject is unwilling or unable to continue, or the parent/legal representative is unwilling or unable to allow the subject to continue in the study.
8. Investigator decides that withdrawal from further participation would be in the subject's best interest.
9. Subject has a prolongation or worsening of overall seizure duration, frequency, type, or pattern considered by the investigator as serious enough to warrant discontinuation from the study.

10. Subject uses rescue medication in excess of that permitted by the protocol.
11. Subject needs any alteration in AED daily dose or VNS settings.
12. In the case of liver function test (LFT) results of transaminases (AST, ALT, or both) $\geq 3x$ ULN to $< 5x$ ULN and total bilirubin $\geq 2x$ ULN or transaminases (AST, ALT, or both) $\geq 5x$ ULN, LCM must be immediately discontinued and the subject withdrawn from the study. The LFTs will be repeated as soon as possible, and in no case > 1 week later.
13. For subjects ≥ 6 years of age, subject has actual suicidal ideation as indicated by a positive response ("Yes") to either Question 4 or Question 5 of the "Since Last Visit" version of the C-SSRS. The subject should be referred immediately to a Mental Healthcare Professional and must be withdrawn from the study.

Subjects **may** be withdrawn from the study if any of the following events occur:

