8.4.1 Taper Period

For subjects who do not enroll in the open-label study (SP848), a 2- to 4 week (depending on dose achieved) Taper Period will be scheduled. For subjects completing the full duration of the Maintenance Period, the Taper Period will begin at Week 19 (±2 days). For subjects who do not complete the full duration of the Maintenance Period, the Taper Period will begin earlier, at the time that they end the Maintenance Period. Please refer to Section 7.2 for details of the taper schedule. Taper of LCM may not be required for some subjects who discontinue study medication prematurely, depending on the treatment option selected by the investigator in consultation with the subject and/or parent/legal representative. These subjects should complete Visit 9/Early Termination Visit and then complete the Safety Follow-Up Visit 2 weeks (±2 days) after the final dose of LCM and a Safety Follow-Up Telephone Contact 30 days (-1/+3 days) after the final dose of LCM.

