#### **4.2.2 Missing data**

With respect to AEs, events with missing intensity will be assumed to be severe. Events with missing relationship to LCM per the investigator will be assumed to be related.

To assess the change and percent change in seizure days for any generalized seizures from the Baseline Period to the Maintenance Period for subjects who prematurely discontinue the study, a

last observation carried forward convention will be applied in the following manner to obtain an estimate for the Maintenance Period:

- Subjects discontinued prematurely during the Titration Period: estimates will be calculated using all available data in the Titration Period and carried forward for the Maintenance Period.
- Subjects discontinued prematurely during the Maintenance Period: estimates will be calculated using all available data in the Maintenance Period and carried forward for the entire Maintenance Period.
- Subjects completing the Maintenance Period: estimates will be calculated using all data from the Maintenance Period.

Missing values for other safety or preliminary efficacy variables will be not imputed.

No imputation of missing values associated with an individual date or visit is planned, with the exception of partial date information for AEs and medications in order to determine whether they are treatment-emergent or concomitant, respectively, and for medical resources to define in which study period these were used. For details see Section 4.2.3.

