### 8.1.2 Generalized seizures

Days with any generalized seizures per 28 days (GSD/28d) will be based on the seizure diary and will be derived separately for the Baseline Period, the Titration Period, and the Maintenance Period. Basis for the calculation will be the number of days with at least 1 generalized seizure (GSD) (absence, myoclonic, clonic, tonic, tonic clonic, atonic, partial evolving to secondarily generalized) during the considered study period and the number of days in the considered study period for which seizure information was provided (D):

$$\text{GSD/28d} = \text{GSD} \times (28/\text{D})$$

The days with any generalized seizures per 28 days will only be derived for subjects who completed or discontinued during the respective study period. For subjects who discontinued during the Titration Period, the missing value of the Maintenance Period will be imputed as described in Section 4.2.

Descriptive statistics will be provided for actual values and changes from Baseline for days with any generalized seizures per 28 days by study period. This summary will be repeated by syndrome subgroups (as described in Section 4.8).

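### Titration and Maintenance run to the ET date even when lacosamide stopped earlier, so drug-free diary days can enter the primary seizure-day rate

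*SAP*

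**What the plan says.** **Period limits.** SAP 3.2.3 defines Titration as running "from the date of first dose of LCM to the date of Visit 6 or the date of ET, whatever occurs first", and Maintenance as running "from the day after the date of Visit 6 to the date of Visit 9/ET". Dosing matters only as a fallback: "If Visit 9/ET is missing the Maintenance Period ends at the date of last dose of LCM". Titration has a similar fallback when Visit 6 and ET are both missing. Under SAP 3.2.1, an unqualified reference to the last dose includes taper doses.

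**Seizure-day rate.** SAP 8.1.2 divides generalized seizure days by "the number of days in the considered study period for which seizure information was provided (D"). It sets no condition that the child was still taking LCM. For withdrawals during Titration, SAP 4.2.2 says "estimates will be calculated using all available data in the Titration Period and carried forward for the Maintenance Period".

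**EEG.** SAP 8.1.1 summarizes discharges by visit, not by period. SAP 4.2.1 reassigns ET assessments to the next visit at which that assessment was due.

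**Stopping LCM.** Protocol 8.3.4 places the ET visit before taper and dispenses taper supply there. Protocol 6.3, criterion 12 (liver tests), says "LCM must be immediately discontinued and the subject withdrawn from the study". Protocol 8.4.1 adds: "Taper of LCM may not be required for some subjects who discontinue study medication prematurely". Neither document gives a maximum interval from last dose to ET.

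**The concern.** Two children who stop LCM on the same day can get different period ends, depending only on whether they attend ET. For the child who attends, the days between last dose and ET are averaged into a rate that is read as the experience on LCM. If that child left during Titration, the blended rate then stands in for 12 weeks of Maintenance.

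The bias can go either way. If LCM was worsening seizures and they settle after stopping, the harm is diluted. If LCM was helping, the benefit is diluted. If abrupt stopping provokes seizures, they are counted as seizures on LCM.

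This matters because change in generalized seizure days is a primary safety variable, and Protocol 5.4 says the study should identify syndromes that LCM may exacerbate. SAP 4.8 presents syndrome subgroups with as few as four subjects, where one child carries real weight. SAP 8.4 already computes exposure from the last dose within the period, so exposure and seizure rate can cover different days for the same child.

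**Working it through.** The plan gives no figure to reproduce: there is no sample size calculation and no assumed withdrawal rate. The check applies the SAP 8.1.2 formula twice, once with the period run to ET and once cut at the last dose.

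**Inputs from the documents**
- Formula: GSD/28d = GSD × 28/D (SAP 8.1.2).
- Period ends: SAP 3.2.3. Carry-forward: SAP 4.2.2. ET mapping: SAP 4.2.1.
- Safety Follow-Up Visit 14 ± 2 days after the final dose and, without taper, after ET (Protocol 8.4.1). If that order is kept, the gap from last dose to ET is at most about 16 days.
- Adult half-life about 13 h (Protocol 2).

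**Assumptions**
- Baseline 14, on-drug 20 and off-drug 14 seizure days per 28.
- Stop days and gaps as in the table.

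**One child.** Fourteen days on drug contribute 14 × 20/28 = 10 seizure days. A 7-day gap contributes 7 × 14/28 = 3.5.
- To ET: 13.5 × 28/21 = 18.0, a change of +4.0, or 4/14 = +28.6%.
- Cut at last dose: 10 × 28/14 = 20.0, a change of +6.0, or 6/14 = +42.9%.

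In general the shift is (gap/D) × (off-drug rate − on-drug rate). With the cut, the change is +42.9% in every row below.

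| Days on drug + gap | Drug-free share of D | Change recorded to ET |
|---|---|---|
| 7 + 3 | 30.0% | +30.0% |
| 7 + 7 | 50.0% | +21.4% |
| 7 + 14 | 66.7% | +14.3% |
| 14 + 7 | 33.3% | +28.6% |
| 28 + 14 | 33.3% | +28.6% |
| 70 + 7 (Maintenance) | 9.1% | +39.0% |
| 70 + 14 (Maintenance) | 16.7% | +35.7% |

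The dilution also applies to benefit. With 7 on-drug days per 28 and the 14 + 7 pattern, the recorded rate is (7 × 14 + 14 × 7)/21 = 9.33. That is −33.3% instead of −50.0%.

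**Group mean.** The 14 + 7 child shifts by 20 − 18 = 2 days per 28. That is 2/50 = 0.04 in the whole study and 2/4 = 0.5 in a four-subject syndrome group. For drug-free shares of 0.10 to 0.67, the shift in a 50-subject mean is k/50 × share × 6 for k affected children:
- k = 1: 0.01 to 0.08
- k = 2: 0.02 to 0.16
- k = 5: 0.06 to 0.40
- k = 10: 0.12 to 0.80

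**EEG.** The 24-hour EEG is scheduled at Visits 2, 6 and 9/ET. Under SAP 4.2.1, an ET recording before Visit 6 becomes a Visit 6 value and so enters the primary EEG variable. One after Visit 6 becomes a Visit 9 value, which feeds only a preliminary efficacy variable. Recording starts the morning before the ET visit (Protocol 8.3.4). At a 13 h half-life, residual drug is 0.5^(24/13) = 28% at 24 h, 8% at 48 h and 2% at 72 h after the last dose.

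**The case against.** The strongest reply is that the protocol normally keeps children on LCM until ET. Supplies are returned and taper doses dispensed at that visit, and the no-taper option is compatible with a last dose at ET. Only the liver rule among the quoted texts clearly stops LCM beforehand; Protocol 11.1.6 (pregnancy) also allows an immediate stop. This stands, and it limits the point to children whose last dose precedes ET.

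A reader might infer that the children withdrawn for worsening seizures are the ones affected. The documents do not support that: criterion 9 in Protocol 6.3 carries no instruction to stop at once, so those children would ordinarily reach ET still on LCM. A reader might also infer that both primary variables are affected throughout both periods. They are not. The period definition does not drive the EEG summaries, and a Maintenance ET EEG never reaches the primary EEG variable.

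Using all data to ET is also a defensible choice. It keeps seizures after abrupt stopping in view, and some drug remains for the first days. Listings mark post-dose days, and treatment-emergent events are collected to 30 days after the last dose. This argues for keeping the to-ET summary, but not for having it alone, because neither listings nor event tables correct the seizure-day rate.

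**Conclusion.** The point holds in a limited form. As written, any diary days between last dose and ET enter the primary seizure-day rate, and for Titration withdrawals they carry into the Maintenance value. A post-drug EEG can reach the primary EEG variable only when the child leaves before Visit 6.

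The number of children affected cannot be found from the documents and is probably small. The effect on the overall mean is then small too: at most 0.16 days per 28 for one or two children under the assumed rates. It can be material for one child or a small syndrome group. In the 14 + 7 example the child drops below the 30% increase cut in SAP 9.2, an exploratory efficacy table, but stays above the 25% listed in SAP 2.2.2.2.

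The sizes rest on assumed seizure rates and gaps, including a return to baseline after stopping. The half-life is an adult value. The study is descriptive, so no test or decision rule is affected.

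**What to change.** - **SAP 3.2.3 and 8.1.2.** For the on-treatment seizure-day rate, end each period at the earlier of the visit date (Visit 6, Visit 9 or ET) and the last LCM dose on or before that visit, excluding taper doses. Apply the same rule when the visit is missing, so that the fallback cannot extend a period into taper. Tying the dose to the visit date also avoids the circularity in SAP 3.2.1, where the Treatment Period last dose is itself defined by the periods.
- **SAP 4.2.2.** Carry forward the on-treatment Titration rate.
- **Supportive summary.** Keep the to-ET version, so that seizures after stopping remain visible.
- **SAP 4.2.1 and 8.1.1.** Flag ET EEGs recorded after the last dose, list the days since that dose, and show the Visit 6 summary with and without them.

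The cost is wording and programming: one extra seizure-day summary and a few EEGs shown separately. Children dosed up to Visit 9 are unaffected.

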LCM=lacosamide; Max=maximum; Min=minimum

^a Titration step to achieve a dose not previously administered^b Titration step subsequent to a back-titration

Note: Asymmetrical dosing with no more than 50mg difference between morning and evening doses will be allowed for subjects taking tablets who require back-titration in a 50mg increment (ie, only 50mg and 100mg tablets are available)

There is no limit to the number of back-titration steps or dose holds allowed and all are at the investigator's discretion; however, subjects must achieve the minimum LCM target dose for their body weight category by the end of the Titration Period. If it becomes apparent that a subject will not be able to reach the minimum target dose, then the subject should be withdrawn from the Titration Period and enter the Taper Period.

Subjects who have LCM titrated to a higher dose not previously administered should remain at that dose for ≥7 days unless a back-titration step is required based on tolerability. Subjects who have LCM back-titrated must remain on the lower dose for ≥3 days (in order to reach steady state) before a subsequent dose increase. After back-titration, subjects who return to a higher dose previously administered must maintain that dose for ≥3 days before subsequent titration to a higher dose.

As outlined in Table 7-3, subjects will be required to achieve and maintain at least a minimum LCM dose for at least the final 3 days of Week 6 to be eligible for entry into the Maintenance Period. Subjects may have a back-titration step as late as the last day of Week 6, as long as the minimum target dose is maintained.

Table 7–3: Required LCM dose for at least the final 3 days of Week 6

Body weight category (formulation)	LCM for at least the final 3 days of Week 6	
	Minimum	Maximum
<50kg (oral solution)	4mg/kg/day	12mg/kg/day
≥50kg (tablets/oral solution)	200mg/day	600mg/day

LCM=lacosamide

Eligible subjects (those who reach and maintain at least the minimum LCM dose for at least the final 3 days of the Titration Period) will enter a 12-week Maintenance Period at the dose they achieved at the last day of Week 6. The LCM dose will remain stable throughout the Maintenance Period. Subjects who require a change in dose during the Maintenance Period

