#### **3.2 General study level definitions**

##### **3.2.1 Last dose of LCM**

Unless otherwise noted, all references to the last dose of LCM in this SAP refer to the last dose of LCM within the study (eg, including the Taper Period). The last dose of LCM during the Treatment Period will be defined as the last dose during the Titration and Maintenance Periods.

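### SAP 3.2.3 starts Maintenance the day after Visit 6 without the protocol's entry condition, so a child who does not qualify can be analysed as a Maintenance subject when ET is dated later or is missing

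*SAP*

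**What the plan says.** **Period boundaries (SAP 3.2.3).** Titration runs from first dose "to the date of Visit 6 or the date of ET, whatever occurs first". Maintenance then runs "from the day after the date of Visit 6 to the date of Visit 9/ET". Each period has a fallback end: "If Visit 6 and ET are missing the Titration Period ends at the date of last dose of LCM", and "If Visit 9/ET is missing the Maintenance Period ends at the date of last dose of LCM". There is no fallback for a missing Maintenance start and no dose condition. SAP 3.2.1 says that, unless otherwise noted, last dose counts taper doses. It gives a separate term for the last dose of the Treatment Period, but the fallbacks in 3.2.3 do not use that term.

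**Entry to Maintenance (Protocol 7.2, Table 7-3).** Subjects must hold at least a "minimum LCM dose for at least the final 3 days of Week 6 to be eligible for entry into the Maintenance Period". A child who will not reach it is to be withdrawn from Titration and enter Taper.

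**Seizure-day value (SAP 4.2.2 and 8.1.2).** The rate is seizure days × 28/D, where D is the number of days in the period with diary information. Titration dropouts have their Titration estimate carried forward. For Maintenance dropouts, "estimates will be calculated using all available data in the Maintenance Period and carried forward for the entire Maintenance Period". Completers use Maintenance data only. SAP 8.1.2 adds: "For subjects who discontinued during the Titration Period, the missing value of the Maintenance Period will be imputed as described in Section 4.2". SAP 4.2.2 plans no imputation for an individual date or visit, apart from partial dates for AEs, medications and medical resources.

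SAP 3.9 declares no change from the protocol-defined analyses.

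**The concern.** In the protocol, attending Visit 6 and entering Maintenance are different events. In the SAP a Visit 6 date is enough. The dose condition is judged on the last days of Week 6 and Visit 6 falls at the end of that week, so failure may first be established at Visit 6 itself. The ET visit has its own 24-hour EEG, started the previous morning, and assessments not done at Visit 6 (complete examinations, endocrinology, plasma concentrations, BRIEF, PedsQL). An ET dated a day or more after Visit 6 is therefore plausible.

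The boundary feeds several outputs:
- the second primary variable (change in generalized seizure days);
- the responder and worsening proportions in SAP 9.2;
- TEAEs by period (SAP 8.2.2);
- Maintenance exposure and mean daily dose (SAP 8.4), which would take in sub-minimum or taper doses.

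Syndrome subgroups are shown with as few as 4 subjects (SAP 4.8), so one misassigned child can move a responder proportion by 1/4, or 25 percentage points.

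**Working it through.** The plan gives no figure to reproduce. The check applies SAP 3.2.3 literally to date patterns.

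**Assumed dates.** First dose is day 1, Visit 6 is day 43 and Visit 9 is day 127.

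**Rules.** Titration end = the earlier of Visit 6 and ET; if both are missing, the last dose. Maintenance days = (Visit 9/ET date, or last dose if that is missing) − Visit 6 date.

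| Pattern | Titration days | Maintenance days |
|---|---|---|
| Completer | 43 | 127 − 43 = 84 |
| Not qualified, ET on the Visit 6 date | 43 | 0 |
| Not qualified, ET 1, 3 or 7 days later | 43 | 1, 3 or 7 |
| Not qualified, ET missing, 2-week taper | 43 | 57 − 43 = 14, all taper |
| Not qualified, ET missing, 4-week taper | 43 | 71 − 43 = 28, all taper |
| Not qualified, ET missing, no taper | 43 | 0 |
| Withdrawn, ET day 35, no Visit 6 | 35 | none; carry-forward works as intended |
| Completer, no Visit 6 date, enters SP848 | 127 | start undefined |
| Completer, no Visit 6 date, 4-week taper | 127 + 28 = 155 | start undefined |

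These day counts are upper limits for D, because D counts only days with diary information.

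**Effect of one seizure day on the 28-day rate** = 28/D:
- D = 1: 28.0
- D = 3: 9.33
- D = 7: 4.0
- D = 14: 2.0
- D = 28: 1.0
- D = 43 (Titration): 0.65
- D = 84 (full Maintenance): 0.33

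**Precision, illustration 1.** Assume seizures on 30% of days (0.3 × 28 = 8.4 per 28 days), independent between days. SE = 28 × √(0.3 × 0.7/D).
- D = 42 (the planned 6 weeks): 28 × √0.005 = 2.0.
- D = 3: 28 × √0.07 = 7.4.
- The chance of no seizure day, scored as a 100% reduction, is 0.7³ = 34% for D = 3 and 70% for D = 1.

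**Precision, illustration 2.** Inclusion criterion 5 requires at least 2 events in the 6-week Baseline. Assume exactly 2, on separate days, with an unchanged rate and independence between days.
- Baseline rate = 2 × 28/42 = 1.33.
- With D = 3, the chance of no seizure day is (40/42)³ = 86%, scored as −100%.
- One seizure day gives 9.33, a change of (9.33 − 1.33)/1.33 = +600%.

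**Completer without a Visit 6 date.** All treatment is classed as Titration. The completer bullet of SAP 4.2.2 needs Maintenance data, and the carry-forward bullets cover only subjects who discontinued. No Maintenance value can be derived.

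**The case against.** The strongest reply rests on a sentence in SAP 8.1.2, repeated in 9.2: the rate is derived only for subjects who completed, or discontinued during, the period in question. Protocol 7.2 classes a child who cannot reach the minimum dose as withdrawn from Titration. If that status is taken from the disposition record, no Maintenance value is derived, the value is missing, and Titration data are carried forward correctly. The SAP permits this reading, so it is not established that the Titration data are discarded. But the SAP never says whether discontinuing during Titration is judged by period dates or by disposition, so two programmers could produce different primary results. The sentence also does nothing for the TEAE and exposure tables, which follow the period dates.

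The scenario is also narrow. The minimum dose is the Week 2 step in Table 7-1, and the protocol directs withdrawal once failure becomes apparent. Many such children would have an ET visit and no Visit 6, which SAP 3.2.3 handles properly. A completer without a Visit 6 date should be rarer still: only Visits 4 and 5 are optional, and Visit 6 dispenses the first Maintenance supply. This limits the likely number of cases. It does not supply the missing rule, and the Data Evaluation Meeting in SAP 3.4 reviews important deviations, not period assignment.

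**Conclusion.** The point holds in conditional form and should be corrected. SAP 3.2.3 lacks the protocol's entry condition. With a recorded Visit 6 and a later ET, or a missing ET with dosing continuing into taper, it labels non-Maintenance days as Maintenance. On a date-based reading, those days become the child's value for a primary variable.

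A reader might infer more than the documents support:
- **Every child who fails the dose test at Visit 6 becomes a Maintenance subject.** Not so. Titration also ends at ET if that comes first, and an ET on the Visit 6 date, or in place of Visit 6, gives no Maintenance days.
- **Maintenance drop-out is inflated in the disposition table.** SAP 5.1 does not say that disposition by period is counted from dates.

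The day counts rest on assumed visit dates. The SEs and probabilities rest on assumed seizure rates and independence between days. The number of children affected cannot be computed from the documents. The study is descriptive, with about 50 subjects planned, so the main risk is to small subgroups and to individual extreme values, not to a formal test.

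**What to change.** Amend SAP 3.2.3 as follows:

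1. Define a Maintenance Period only for subjects documented as having entered Maintenance under the protocol's existing entry rule.
2. For subjects who attended Visit 6 but did not enter, define no Maintenance Period. End Titration at ET or, if ET is missing, at the last dose before taper. Classify them as discontinued during Titration and apply the first carry-forward bullet of SAP 4.2.2. Stopping Titration at Visit 6 instead would leave the days from Visit 6 to ET, and any AEs in them, in neither period.
3. If Visit 6 is missing but a later Maintenance visit exists, end Titration on the scheduled Visit 6 day and start Maintenance the next day.
4. If Visit 9/ET is missing, end Maintenance at the last pre-taper dose.

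State in SAP 4.2.2, 8.1.2 and 9.2 that the period of discontinuation follows this classification.

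The cost is a few sentences and one programming flag built from dosing and disposition data already collected. No clinical rule changes.
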